14.4.2 Secondary efficacy variables

Secondary efficacy variables are:

- Safety (percentage of subjects with at least one TEAE);
- Incidence of adverse events.

14.4.3 Other efficacy variables

Other efficacy variables are:

- VAS POM over the initial 12-hours (VAS AUC₀₋₁₂), 24-hours (VAS AUC₀₋₂₄), 36-hours (VAS AUC₀₋₃₆), 48-hours (VAS AUC₀₋₄₈), 60-hours (VAS AUC₀₋₆₀), 72-hours (VAS AUC₀₋₇₂), and 120 hours (VAS AUC₀₋₁₂₀);
- Change of VAS POM at hours 12, 24, 36, 48, 60, 72 and 120 from baseline (BL);
- VAS POM over the initial 72-hours (VAS AUC₀₋₇₂) in the subgroups “sprain/strain” and “contusion”.
- Change of Algometric Tenderness (N/cm²) at hours 12, 24, 36, 48, 60, 72, and 120 from baseline;
- Algometric Tenderness (N/cm²) over the initial 12-hours (N/cm² AUC₀₋₁₂), 24- hours (N/cm² AUC₀₋₂₄), 36-hours (N/cm² AUC₀₋₃₆), 48-hours (N/cm² AUC₀₋₄₈) 60-hours (N/cm² AUC₀₋₆₀) and 120 hours (N/cm² AUC₀₋₁₂₀);
- Ratio of algometry injured/contralateral sites over 72 hours and 120 hours (N/cm² Ratio AUC₀₋₇₂ and N/cm² Ratio AUC₀₋₁₂₀);

	Trial Substance:	BAY H6689	Study No.:	21559
	Short Title:	Acute Soft Tissue of the Lower Extremities	Sponsor:	BAYER HEALTHCARE LLC.

- Algometry over the initial 72-hours (N/cm^2 AUC_{0-72}) in the subgroups “sprain/strain” and “contusion”.
- Percent of subjects with no (zero) VAS POM at 120 hours;
- Global assessment of treatment efficacy at 24 hours, 48 hours, 72 hours, and 120 hours by patients using a 5-point scale (0=none, 1=poor, 2=fair, 3=good, 4=excellent);
- Global assessment of treatment efficacy at 72 hours in the subgroups “sprain/strain” and “contusion”.
- Change of VAS PAR at hours 12, 24, 36, 48, 60, 72 and 120 from baseline (BL).

Figures will show the time course of outcomes by treatment group for the key quantitative outcomes VAS POM, Change of VAS POM, Algometric Tenderness and Change of Algometric Tenderness. A Kaplan-Meier plot of zero VAS POM scores will also be performed, with the first time point with zero VAS POM and all subsequent VAS POM scores are zero. The primary outcome will also be summarized by center (if there is evidence of a treatment-by-center interaction), sex, age and race but without formal statistical comparisons of treatments.

For quantitative outcomes assessed each null hypothesis will be tested with an analysis-on-covariance (ANCOVA) model including treatment group and center as main effects, and the baseline value as covariate (those outcomes for which there is a baseline). The model will be fit both with and without the treatment-by-center interaction. The primary model will be the model without the interaction. If the treatment/center interaction is statistically significant ($p < 0.05$), additional ANCOVAs will be run to identify the center(s) driving the interaction and to lay out the evidence for efficacy among the centers whose results are concordant and centers driving the interaction. ANCOVA outputs will be presented in the Statistical Appendix for the primary and various secondary outcomes to allow an outside reviewer to assess the acceptability of the primary statistical model.

The treatment effects will be estimated as mean differences between the active and placebo groups and between the two active groups with 95% confidence intervals.

The percentage of subjects with no VAS POM at 120 hours will be analyzed by means of Fisher's exact test.

The ordinal outcome (global assessment of treatment efficacy)) will be analyzed by the Cochran-Mantel-Haenszel test of general association, stratified by center and also by subgroup (strain/sprain, contusion).

Statistical test results for secondary variables will only be interpreted exploratorily.

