1 in 5 chance of receiving the placebo treatment. Treatment consists of a twice daily application (approximately 12 hours apart) of the assigned topical gel over 5 consecutive days, beginning on the evening of Day 1 and ending (last application) on the morning of Day 6 (total of 10 applications). All treatment applications will be performed by study staff at the site. After the first treatment, two visits each day for five consecutive days are required. Patients who experience a treatment failure can have the option of taking rescue medication for pain relief.

During the screening/baseline and follow-up treatment visits, tenderness will be measured by the pressure required to elicit a response. Pain on movement will also be rated by the subject using a 100 mm visual analogue scale.

Approximately 100 participants will be screened to achieve 75 randomized to study intervention for an estimated total of 30 evaluable participants per each active treatment and 15 participants in the placebo treatment.

Study Duration: 6 days

Treatment Duration: 6 days

Visit Frequency: After the first treatment, two visits each day for five consecutive days

Condition/Disease: Soft tissue injury, either a sprain/strain or contusion

Study Hypothesis: Topical naproxen gel, 10% effectively relieves tenderness to pressure in patients with acute soft tissue injuries

Health Measurement/Observation: Algometry measurements for tenderness and Visual Analog Scales for pain will occur pre and post topical treatment.

Number of Participants: Approximately 100 participants will be screened to achieve 75 randomized to study intervention for an estimated total of 30 evaluable participants per each active cohort and 15 participants in the placebo cohort.

Intervention Groups: Participants will be randomized in 2:2:1 fashion and stratified by injury type with at least 25 participants in the Sprain/Strain cohort and at least 50 participants in the Contusion cohort.

Data Monitoring/Other Committee: No

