8.1.2 Baseline Visit 1 - (Day 1)

Patients will undergo baseline pain and tenderness testing to determine eligibility for randomization. All patients must score at least 50 on the 0 – 100 mm visual analog scale (VAS) for POM and have algometric measurement values on the injured site of $\leq 50\%$ of the respective value at the contralateral site in order to qualify for treatment. Additionally, the absolute tenderness sensitivity of the contralateral site must be at least 2.5 N/cm^2 . The investigator will stratify patients into 2 injury cohorts. One cohort is contusion cohort and the other is the sprain/strain cohort. The contusion cohort will enroll at least 50 patients and the sprain/strain cohort will enroll at least 25 patients.

The site will randomize Investigational Medicinal Product (IMP or treatment kit) based on computer generated randomization schedule stratified by injury type (either contusion or sprain/strain cohorts).

Patients entering the Treatment Phase are randomized in a 2:2:1 fashion into one of three blinded treatments:

- Naproxen Topical Gel, 10%, every 12 hours for 5 days
- Diclofenac Diethylamine Topical Gel, 2.32% every 12 hours for 5 days
- Placebo Topical Gel every 12 hours for 5 days

Patients will be reminded to discontinue use of all pain medications including supplements, use of topical heat or cold, and other products of topical application once the patient is deemed eligible to participate.

The investigator or designee will mark the injured lower extremity with a water-resistant pen so that the treatment area is consistently targeted through the Treatment Phase. After randomization, the ***first*** topical treatment will be applied the evening of Day 1. The topical treatment will be weighed on a digital scale, then applied by an unblinded study staff at the site who is not responsible for adverse events, global assessments, pain and tenderness measurements. Patients will wear a blindfold during treatment so that the identity of the IMP is blinded. Patients will be instructed to return approximately 12 hours to the site for their ***second*** treatment. The nominal repeat dosing times will be established for the rest of the study that conform to the dosing time established on Day 1.

Rescue medication will be dispensed. If the patient decides to take rescue medication prior to the next treatment, the patient will be instructed to complete the Global Assessments prior to taking the rescue medication.

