6 SAMPLE SIZE

This is a proof-of-concept study and therefore a specific statistical power calculation cannot be applied, however, assuming a comparable effect of the test gel vs. diclofenac – as suggested by pharmacological studies, reference is made to similar studies (Predel, Br J Sports Med 2004;38:318–323), in which the standardized effect sizes of Algometry AUC 0-72 and POM VAS AUC 0-72 were over 1; with 30:15 patients, a drop-out rate of 10 %, and a two-sided significance level $\alpha = 5\%$, a power $1 - \beta$ of about 80 % is reached.

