14.7 Multiplicity

In this Phase II and proof-of-concept study all endpoints will be summarized descriptively by treatment. Statistical tests will be conducted at the significance level of 5 % and no multiplicity adjustments will be made.

	Trial Substance:	BAY H6689	Study No.:	21559
	Short Title:	Acute Soft Tissue of the Lower Extremities	Sponsor:	BAYER HEALTHCARE LLC.

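### The zero-pain endpoint at 120 hours is tested by an unstratified Fisher's exact test although randomisation is stratified by injury type; the test is valid, but an equally exact stratified test can have more power

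*SAP*

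**What the plan says.** For the binary efficacy endpoint, SAP 14.4.3 reads: "The percentage of subjects with no VAS POM at 120 hours will be analyzed by means of" Fisher's exact test. No stratum is named, and the text does not say whether the test is applied to the three arms together or to pairs of arms.

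Protocol 8.1.2 has patients allocated from a "computer generated randomization schedule stratified by injury type (either contusion or sprain/strain cohorts". The Synopsis adds the planned sizes: "Participants will be randomized in 2:2:1 fashion and stratified by injury type with at least 25 participants in the Sprain/Strain cohort", and at least 50 in the contusion cohort.

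The next sentence of SAP 14.4.3 analyses the global efficacy rating by a Cochran-Mantel-Haenszel (CMH) test stratified by center and also by injury subgroup. SAP 14.5 does the same for global tolerability and the sensory questions.

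Protocol 9.4.4 lists the zero-pain endpoint among the other endpoints and prescribes no test. On error control, SAP 14.7 says: "Statistical tests will be conducted at the significance level of 5 % and no multiplicity adjustments will be made". SAP 14.4.3 treats tests on secondary variables as exploratory.

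**The concern.** Among the categorical outcomes that the SAP tests, this is the only one that ignores the factor used to stratify randomisation, and no reason is given. If contusions and sprains/strains become pain-free at different rates, pooling them adds between-stratum variation to the comparison and makes Fisher's test more conservative. Small numbers do not force the choice, because an exact test can also be stratified. At stake is some avoidable loss of power on one exploratory endpoint, in a trial with about 15 placebo patients that is meant to guide a development decision.

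**Working it through.** **Plan's own figure.** The documents give no power for the zero-pain endpoint. The only power statement, about 80%, concerns the two AUC 0-72 endpoints at a standardised effect over 1, "with 30:15 patients, a drop-out rate of 10 %, and a two-sided significance level" of 5%. At an effect of exactly 1, a two-sample t-test gives 82.3% at 27:13 and 81.8% at 26:13, so that figure is reproduced. It says nothing about the binary endpoint.

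**Inputs from the documents.**
- Allocation is 2:2:1 with 50 contusions and 25 sprains/strains. Naproxen:placebo is then 20:10 in contusion and 10:5 in sprain/strain.
- With 10% dropout these become 18:9 and 9:4.5. The last is taken as 9:4, which gives 27:13 in total.
- Tests are two-sided at 5%.

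**Assumed inputs.** Zero-pain rates are given neither overall nor by injury type, so a range is shown.

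**Tests compared.**
- *Fisher.* Given M responders in total, P(X = x) = C(27, x)·C(13, M − x) / C(40, M), where X is the number of naproxen responders.
- *Stratified exact.* Given m1 responders among contusions and m2 among sprains/strains, S = X1 + X2. Each Xi is hypergeometric within its stratum, and the distribution of S is the convolution of the two.
- In both, the two-sided p-value sums the probabilities no larger than that of the observed result.
- Power is the summed binomial probability of all tables with p ≤ 0.05, over the 19 × 10 × 10 × 5 = 9,500 possible tables. This is full enumeration, without simulation error.

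**Power, naproxen against placebo, 18:9 and 9:4** (rates are naproxen/placebo):

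| Contusion | Sprain/strain | Fisher | Stratified exact | Gain (points) |
|---|---|---|---|---|
| 80/40% | 30/5% | 50.7% | 57.3% | 6.6 |
| 70/30% | 30/5% | 51.1% | 53.5% | 2.4 |
| 60/20% | 50/15% | 61.6% | 61.7% | 0.1 |
| 60/20% | 60/20% | 66.2% | 66.2% | 0.0 |

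**Type I error, same sizes.** At a common null rate of 50%, both tests reject in 4.2%. At null rates of 40% (contusion) and 5% (sprain/strain), Fisher rejects in 2.0% and the stratified test in 3.3%. Both hold the level; Fisher is the more conservative when the strata differ.

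**Wider range, no dropout (20:10 and 10:5), odds ratio 6 in each stratum.** By placebo rate in contusion and sprain/strain, power for Fisher and stratified exact is:
- 20% and 20%: 66.9% and 67.3%
- 30% and 10%: 60.9% and 65.8%
- 50% and 10%: 52.1% and 59.2%
- 10% and 60%: 36.0% and 54.3%

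The last case is extreme, and nothing in the documents points to it.

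**What pooling does to the effect measure.** In the first row of the table the pooled rates are (18 × 0.80 + 9 × 0.30)/27 = 63.3% and (9 × 0.40 + 4 × 0.05)/13 = 29.2%.
- The pooled odds ratio is (63.3/36.7)/(29.2/70.8) ≈ 4.2, against 6.0 and 8.1 within the strata. The odds ratio is attenuated.
- The difference in percentages is 34.1 points, against a weighted stratum average of (2 × 40 + 25)/3 = 35.0. The small gap comes from rounding 4.5 down to 4, so the difference is essentially preserved.

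**The case against.** The strongest reply is that this is a preference about efficiency and that the plan contains no error. Fisher's test keeps its level after stratified randomisation, neither document is contradicted, and no rate in the documents shows that injury type is prognostic for zero pain. With moderate stratum differences the gain is a tenth of a point. All of this stands, and it limits the size of the point.

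A reader might infer more than the documents support:
- *That Fisher's test is wrong after stratified randomisation.* It is not; it is at worst conservative.
- *That pooling biases the comparison of percentages.* With allocation balanced within strata it does not; what shrinks is the odds ratio.
- *That Fisher's test has nothing in its favour.* It needs no assumption of a common odds ratio, and it can be marginally better when injury type is not prognostic: 89.8% against 89.5% at odds ratio 10 with placebo rates of 20% in both strata (20:10 and 10:5). It also guarantees the level, whereas the large-sample stratified CMH test reached 5.1% on a grid of null rates. The exact stratified test keeps that guarantee.

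It can also be said that the ANCOVA models in SAP 14.4.1 and 14.4.3 omit injury type too. That is correct: the omission is not confined to this endpoint. It does not remove the inconsistency among the categorical outcomes.

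**Conclusion.** The point holds as a low-priority improvement. The planned test is valid but ignores the randomisation stratum, and an equally exact test that respects it is available. In the assumed 27:13 scenarios the gain runs from nothing to 6.6 percentage points. It depends wholly on how far zero-pain rates differ between contusion and sprain/strain, which the documents do not say. The figures also assume pairwise testing of naproxen against placebo, 10% dropout spread evenly, and stratum sizes of 50 and 25. Because the endpoint is exploratory, the primary analysis and the stated power of about 80% are unaffected.

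**What to change.** In SAP 14.4.3, replace the sentence on Fisher's test with the following plan:
- For each pairwise contrast (naproxen against placebo, diclofenac against placebo, naproxen against diclofenac), use the exact conditional test stratified by injury type. This also settles whether the test is pairwise or across three arms.
- Do not add center as a stratum. Three sites by two injury types gives six cells for 15 placebo patients, or 2.5 per cell on average, which is too sparse.
- Keep Fisher's exact test as a sensitivity analysis.
- Report the percentage with zero pain by arm and the differences between arms. If an exact common odds ratio with 95% confidence interval is added, state that it is conditional on stratum and assumes the same odds ratio in both injury types. With about four evaluable placebo patients in sprain/strain, that assumption can hardly be checked.

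The cost is one line in the SAP. Injury type is already recorded at screening, so no new data are needed.

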14.5 Safety

The assessment of safety will be based mainly on the frequency of AEs that are treatment-emergent in the Safety Population. Formal statistical tests will not be conducted for differences in safety parameters between treatment groups. Only descriptive analyses will be conducted.

The incidence of all treatment-emergent AEs will be after grouping by body system and preferred term. For each preferred term and summarized over each body system overall, the table will present the number of patients in each treatment group in whom the event occurred and the rate (%) of occurrence. The incidence of all suspected-drug-related AEs will be tabulated similarly. The incidence of all treatment-emergent AEs will also be tabulated by severity

	Trial Substance:	BAY H6689	Study No.:	21559
	Short Title:	Acute Soft Tissue of the Lower Extremities	Sponsor:	BAYER HEALTHCARE LLC.

categories and relationship to the IMP. Seriousness, severity, relationship to IMP duration and outcome will also be listed.

Safety will also be summarized with respect to vital signs as mean levels by visit and change from baseline. Abnormal observations on physical exams will be listed.

The ordinal outcome (global assessment of tolerability) will be analyzed by the Cochran-Mantel-Haenszel test of general association, stratified by center and also by subgroup (strain/sprain, contusion).

Furthermore, the ordinal outcome (sensory questions) will also be analyzed by the Cochran-Mantel-Haenszel test of general association, stratified by center and also by subgroup (strain/sprain, contusion).

Listings of individual data will be presented.

14.5.1 Adverse events

Adverse events will be coded according to MedDRA, Version 24.0.

The incidence of all treatment-emergent AEs will be tabulated after grouping by body system and preferred term. For each preferred term and summarized over each body system overall, the table will present the number of patients in each treatment group in whom the event occurred and the rate (%) of occurrence. The incidence of all suspected-drug-related AEs will be tabulated similarly. The incidence of all treatment-emergent AEs will also be tabulated by severity categories.

14.5.2 Other variables related to safety

Summary statistics for the absolute vital sign value and the changes from baseline will be presented using n, mean, standard deviation, median, minimum, and maximum.

Abnormal observations on physical examinations will be listed.

Furthermore, weight, pregnancy and assessments of fertility data will only be listed.

14.6 Multi-site study

Individual site results will be presented by means of descriptive statistical methods for the demographical and primary efficacy data. Moreover, the treatment-by-site interaction will be assessed by means of an ANCOVA model for the primary variable and other selected secondary variables.

14.7 Multiplicity

In this Phase II and proof-of-concept study all endpoints will be summarized descriptively by treatment. Statistical tests will be conducted at the significance level of 5 % and no multiplicity adjustments will be made.

	Trial Substance:	BAY H6689	Study No.:	21559
	Short Title:	Acute Soft Tissue of the Lower Extremities	Sponsor:	BAYER HEALTHCARE LLC.

14.8 Missing data

- If assessments at any visit for Visits 2 (12 h) through Visit 10 (108 h) are missing, they will be imputed as the average of the preceding and the following assessments. Fractional values will be rounded down (including ordered categorical assessments). If assessment at Visit 11 is missing, the last observation will be carried forward.
- If a patient terminates prematurely,
 - all subsequent visits will be imputed by carrying the last non-missing observation forward,
 - for an adverse event suspected to be study-drug-related, then all subsequent visits will be imputed by carrying the baseline observation forward,
 - for lack of efficacy, all subsequent assessments will be imputed as the worst of all documented assessments,
 - for lack of efficacy or for an adverse event suspected to be study-drug-related and does not complete the global assessment of treatment satisfaction, it will be assigned the worst possible score,
 - If a patient discontinues for any other reason, missing global assessments at Visit 11 will be imputed by the worst possible outcome.
- If a patient assesses efficacy at the site < 6 hours after using rescue medication, imputation will be discussed in the Blind Review Meeting, with consideration given to the frequency of this issue in the database and the elapsed time between rescue and assessment of efficacy.
- If a patient assesses spontaneous pain intensity and spontaneous pain relief at the time of rescue taken because of blunt trauma pain, any assessment conducted in the following 6 h will be replaced by the corresponding assessment done at the time of rescue.
- If the patient provides no post-baseline efficacy data, imputation will be considered in the Blind Review Meeting.

A Blind Review Meeting will take place before unblinding the randomization code. Handling of missing values/censoring/discontinuation, if necessary, will be provided and discussed in the Blind Review Meeting. Additional data handling rules will be specified in the BRM minutes to cover issues not anticipated in the above stipulations.

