8.2.3 Global Assessments of Efficacy and Tolerability

At 24 hours, 48 hours, 72 hours and 120 hours post dose, the patient and the investigator will rate global assessment of the treatment efficacy using a 5-point Likert scale.

Global Efficacy

How would you rate the study medication you received as a pain-reliever?

- 0 = poor
- 1 = fair
- 2 = good
- 3 = very good
- 4 = excellent

At 24 hours, 48 hours, 72 hours and 120 hours post dose, the patient and the investigator will rate global assessment of tolerability (quality of life) using a 5-point Likert scale.

Global Tolerability

Considering all the ways this treatment has affected you since you started in the clinical trial, how well are you doing?

- 0 = poor
- 1 = fair
- 2 = good
- 3 = very good
- 4 = excellent

If the patient completes the Global Assessment not at the time of the scheduled clinic visit (or between visits), then the investigator will complete the Global Assessment at the next scheduled visit.

Planned time points for all efficacy assessments are provided in the SoA and Section [8.1](#).

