9.4.5 Safety Analysis

Safety will be measured by adverse events (AEs) and vital signs. Only descriptive analyses will be conducted on the Safety Population. No imputation will be made for missing safety data. Quantitative data for safety variables will be described by summary statistics for the original data as well as for the differences to baseline when it is appropriate. Frequency tables will be provided for qualitative data. No statistical test will be planned regarding the safety analyses.

Only treatment-emergent AEs will be included in the summary analysis, i.e., AEs that begin or worsen after the first application of Investigational Medicinal Product (IMP). The number and percent of subjects who experience any event and the number of events overall, by System Organ Class, and by Preferred Term will be displayed by treatment group. Tables will also be produced by severity and relationship to IMP. Seriousness, severity, relationship to IMP duration, and outcome will also be listed.

Listings of individual data will be presented.

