5.2 Safety variables

Secondary efficacy variables are:

- Safety (percentage of subjects with at least one TEAE);
- Incidence of adverse events.

The following parameters are recorded to assess the safety of the study drug:

- Adverse events (AEs).
AEs will be documented at Visit 1 to Visit 11.
- Vital signs and body temperature.

	Trial Substance:	BAY H6689	Study No.:	21559
	Short Title:	Acute Soft Tissue of the Lower Extremities	Sponsor:	BAYER HEALTHCARE LLC.

Pulse rate (bpm) and blood pressure (BP_s, BP_d (mmHg) as well as body temperature will be documented at the Baseline Visit (Visit 1), Visit 7, and Final Visit (Visit 11)).

- General physical examination.

Physical examination will be performed at Visit 1 (randomization visit), Visit 2, Visit 4, Visit 6, Visit 8, and Visit 10, as well as when judged necessary by the Investigator.

A general physical examination will be performed at Visit 1 and include the injured extremity and assessments of the Dermatological, Cardiovascular, Respiratory, Gastrointestinal and Neurological systems.

A limited physical examination of the injured extremity will be performed at Visits 2, 4, 6, 8 and 10. Any issues will be described as adverse event.

Examination will include general condition, dermatologic, eyes, ears, nose, throat, neck, thyroid, heart, respiratory system, abdomen, kidneys, skeletal system, extremities, lymphatic system, CNS, neurological conditions and other (to be specified).

- Height and body weight.

Height in centimeters (cm, without shoes) and body weight (kg, in indoor clothing, but without shoes) will be measured at Visit 1. The corresponding Body Mass Index (BMI) will be calculated.

- Pregnancy and assessments of fertility.

Female participants of child-bearing potential will undergo urine pregnancy testing at Visit 1 (prior to first dose) and Visit 10 (prior to last dose).

- Global tolerability

Global tolerability will be assessed by the investigators and the patients according to the following numerical scale at Visits 3, 5, 7, and 11, respectively:

- 0: poor
- 1: fair
- 2: good
- 3: very good
- 4: excellent.

- Sensory questions

During the final visit of the study (Visit 11), patients will be asked two sensory questions related to the IMP they received.

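### The SAP's imputation rules are not limited to efficacy and so reach global tolerability, which the SAP classes as safety, and SAP 14.5 both rules out and orders tests of safety parameters

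*SAP*

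**What the plan says.** **Protocol.** Section 9.4.5 states "Safety will be measured by adverse events (AEs) and vital signs", then "No imputation will be made for missing safety data" and "No statistical test will be planned regarding the safety analyses". Global tolerability is described elsewhere, in "8.2.3 Global Assessments of Efficacy and Tolerability", which sits under the efficacy assessments of section 8.2. Section 6.10.1 makes clear that the term Global Assessments means the efficacy rating and the tolerability rating together.

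**SAP, classification.** Section 5.2 lists vital signs, global tolerability and the sensory questions among the parameters recorded to assess safety. On tolerability it says "Global tolerability will be assessed by the investigators and the patients according to the following numerical scale at Visits 3, 5, 7, and 11", on a scale from 0 (poor) to 4 (excellent).

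**SAP, testing.** Section 14.5 says "Formal statistical tests will not be conducted for differences in safety parameters between treatment groups" and that the analyses will be descriptive only. Further down the same section says "The ordinal outcome (global assessment of tolerability) will be analyzed by the Cochran-Mantel-Haenszel test of general association", stratified by center and by injury subgroup, and orders the same test for the sensory questions.

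**SAP, imputation.** Section 14.8 opens with "If assessments at any visit for Visits 2 (12 h) through Visit 10 (108 h) are missing, they will be imputed as the average". The values averaged are those before and after the gap, and the result is rounded down, ordered categories included. After early termination it carries the last value forward, or the baseline value after a suspected drug-related adverse event. Missing Visit 11 global assessments get the worst outcome after discontinuation for other reasons. No sentence restricts these rules to efficacy.

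**The concern.** Two parts of the SAP cannot be carried out as they stand.

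First, a programmer who follows 14.5 must either leave out the CMH tests, against one sentence, or run them, against another.

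Second, 14.8 covers tolerability. A patient who leaves for a reason unrelated to treatment, with no Visit 11 rating, is recorded as having rated tolerability poor. Nobody gave that rating, and the SAP itself calls the variable a safety parameter.

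Safety is the trial's secondary objective. At stake are a tolerability table that mixes observed ratings with assigned ones, and p-values in a section that says it has none. Two programmers could produce different tables from the same text.

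**Working it through.** The documents give no figure on this point, so the check sets the texts side by side and then sizes the consequence.

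**1. Testing.** SAP 5.2 puts tolerability and the sensory questions among the safety parameters. SAP 14.5 excludes formal tests of safety parameters and then orders them for these two. The contradiction lies wholly within the SAP. Vital signs are not part of it: SAP 14.5 and 14.5.2 give them summary statistics only.

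**2. Reach of the imputation rules.**
- Where 14.8 means efficacy it says so, for example for assessments made soon after rescue medication. Its first two groups of rules carry no such limit.
- It names ordered categorical assessments. The ordinal outcomes in this trial are global efficacy, global tolerability and the sensory questions.
- It names global assessments at Visit 11, and by Protocol 6.10.1 these include tolerability.

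**3. Rules that cannot be computed for tolerability.** It is first rated at Visit 3. There is no baseline rating to carry forward after a drug-related adverse event, and no earlier rating to average with if Visit 3 is missing.

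**4. Vital signs.** They are recorded at Visits 1, 7 and 11. Read literally, a missing Visit 7 value becomes the average of Visits 1 and 11, a missing Visit 11 value is carried forward, and values after a drug-related withdrawal return to baseline (change of zero). Rounding down would turn an average temperature of 36.75 into 36. That oddity suggests the rules were not written with vital signs in mind, but nothing in 14.8 excludes them.

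**5. Size of the imputation effect.** Inputs: 30, 30 and 15 patients (SAP 2); 10% drop-out (SAP 6).
- Active arm: 0.10 × 30 = 3 patients. Placebo: 0.10 × 15 = 1.5, so 1 to 2.
- One imputed poor rating: 1/30 = 3.3 points in an active arm, 1/15 = 6.7 points on placebo.
- At the upper bound: 3/30 = 10 points in an active arm; 2/15 = 13.3 points on placebo.
- If 3 of 30 patients whose last rating was 3 are set to 0, the arm mean falls by 3 × 3/30 = 0.3 on the 0 to 4 scale.

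**6. Number of tests.** Tolerability: 2 raters × 4 visits = 8. Sensory questions: 2. Total 10 at 5%, unadjusted (SAP 14.7). If they were independent, the chance of at least one false positive would be 1 − 0.95^10 = 40%; correlation lowers this.

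**7. Choice of test, if one is kept.** With three arms and five categories, general association has (3 − 1)(5 − 1) = 8 degrees of freedom and ignores the order of the scale. The power figures below come from 2,000 simulated trials per setting, with arms of 30/30/15 and 2, 3 or 6 strata. The placebo shares (10/20/30/25/15% from poor to excellent) and an equal latent shift in both active arms are assumptions, not figures from the documents.

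| Assumed shift (SD) | General association | Row mean score |
|---|---|---|
| 0.5 | 15–16% | 26–29% |
| 0.8 | 36–44% | 61–64% |
| 1.0 | 58–63% | 81–85% |

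With no shift, both tests reject in 4–5% of runs.

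**The case against.** The strongest reply is that the protocol does not treat tolerability as safety. Section 9.4.5 names adverse events and vital signs, section 8.3 lists physical examination, vital signs and pregnancy testing, and tolerability sits under efficacy assessments. This stands. A reader might infer that the protocol directly forbids imputing or testing tolerability; it does not. That conflict exists only because SAP 5.2 reclassified the variable. The contradiction within SAP 14.5 remains either way.

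A reader might also infer that vital-sign results will carry imputed values and p-values. No vital-sign test is planned. Imputation of vital signs is never stated: the protocol's ban is explicit, and the SAP presents itself as an elaboration of the protocol. For vital signs this is an ambiguity to close, not a planned breach.

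Nor do the documents support the reading that imputation would conceal the harm behind a withdrawal. The withdrawal rules fill only later visits. Observed values stay, adverse events are tabulated by severity and relationship, and reasons for discontinuation are summarized and listed.

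Finally, the CMH tests are insensitive rather than invalid, since their simulated type I error is close to nominal. These are also non-primary outcomes in a proof-of-concept trial. Both points stand and limit the severity.

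**Conclusion.** The point holds in this form: SAP 14.5 contradicts itself on testing tolerability and the sensory questions, and SAP 14.8 imputes tolerability because nothing limits it to efficacy. Given the SAP's own classification of tolerability, 14.8 then conflicts with the protocol's ban on imputing safety data.

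The effect is 3.3 points per imputed rating in an active arm and 6.7 on placebo. The counts of 3 per active arm and 1 to 2 on placebo are upper bounds. They assume the planned 10% drop-out occurs in every arm, that every drop-out falls under the other-reasons rule, and that every one lacks a Visit 11 rating. The documents do not give the size of that subset. The power comparison rests on assumed category shares and bears only on which test to use if one is kept.

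Adverse-event tables and the primary endpoint are not affected. Severity is low to moderate.

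**What to change.** 1. Open SAP 14.8 with: *These rules apply to efficacy variables only; safety variables, including vital signs and global tolerability, are not imputed.*
2. Report tolerability as observed counts and percentages by arm, with the number missing.
3. Resolve SAP 14.5 in one of two ways, both acceptable:
   - delete the CMH tests of tolerability and of the sensory questions; or
   - reclassify both as exploratory non-safety outcomes in SAP 5.2, move their tests out of the safety section, and use the row-mean-score CMH test for the ordered tolerability scale.

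The row-mean-score test is proposed for tolerability only. The sensory questions in Protocol 8.2.4 include answers with no place in an order, such as not noticing a scent.

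The cost is SAP wording, made before unblinding. No new data are needed; the first option reduces programming, and the second changes one test statistic.
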